3.4. Dose Adjustment Criteria

Dose adjustment is not permitted in this study.

3.5. Stopping Rules

The study may be terminated at the discretion of Insys Development Company, Inc at any time and for any reason.

4. TREATMENTS

4.1. Treatments Administered

Eligible subjects meeting all study entry criteria will be randomly allocated in a 1:1:1 ratio to one of the following treatments containing active or placebo administered up to 6 doses per day as shown in the table below:

Table 1: Study Treatment Regimens

Treatment group	Day 1						Day 2					
	Dose 1	Dose 2	Dose 3	Dose 4	Dose 5	Dose 6	Dose 1	Dose 2	Dose 3	Dose 4	Dose 5	Dose 6
100 µg	100 µg	100 µg	100 µg	100 µg	100 µg	100 µg	100 µg	100 µg	100 µg	100 µg	100 µg	100 µg
200 µg	200 µg	200 µg	200 µg	200 µg	200 µg	200 µg	200 µg	200 µg	200 µg	200 µg	200 µg	200 µg
Matching Placebo	P	P	P	P	P	P	P	P	P	P	P	P

4.2. Identity of Investigational Product

The investigational product in this study is Fentanyl Sublingual Spray. Each dose of 100 µg or 200 µg is delivered as a single 100-µL sublingual spray.

Fentanyl Sublingual Spray, is a potent opioid analgesic intended for sublingual administration. Fentanyl Sublingual Spray is formulated to be sprayed underneath the tongue to allow for absorption of fentanyl across the sublingual mucosa.

4.3. Method of Assigning Subjects to Treatment Groups

Eligible subjects meeting all study entry criteria will be randomly allocated in a 1:1:1 ratio to 1 of the 3 treatment groups.

The randomization schedule will be computer generated by using a permuted block algorithm and will randomly allocate the investigational produce (IP) to randomization numbers. The randomization numbers will be provided to the drug packager who will prepare blinded drug kits with all twelve (12) doses identified to maintain the drug blinding. The randomization schedule will be prepared by the sponsor or sponsor's representative before the start of the study. No one involved in the study performance will have access to the randomization schedule before official unblinding of treatment assignment. No subject will be randomized into this study more than once.

4.4. Selection and Timing of Dose for Each Subject

This is a randomized study, and treatment assignment is conducted in consecutive order to prevent bias. Randomization will occur on Day 1.

4.5. Blinding and Unblinding Treatment Assignment

All subjects and study personnel involved in the conduct of the study, including data management, will be blinded to treatment assignment with the exception of a specified unblinded statistical programmer from the sponsor or sponsor's representative who will have access to the randomization code. The unblinded study personnel will not otherwise participate in study procedures or data analysis before unblinding of the study data to all study-related personnel.

Study personnel will endeavor to safeguard the integrity of the study blind to minimize bias in the conduct of the study. Treatment unblinding is discouraged if knowledge of the treatment assignment will not materially change the planned management of a medical emergency. Unblinding will be permitted in a medical emergency that requires immediate knowledge of the subject's treatment assignment. If a medical emergency occurs and unblinding is required, the site will contact IXRS for drug assignment. Unblinding should be discussed in advance with the sponsor, sponsor's representative, or medical monitor if possible. For emergency unblinding, study personnel will contact the sponsor or sponsor's representative. If the investigator is not able to discuss treatment unblinding in advance, then he or she must notify the sponsor, sponsor's representative, or medical monitor as soon as possible about the unblinding incident without revealing the subject's treatment assignment. The investigator or designee must record the date and reason for study unblinding in the source document for that subject. In all cases that are not emergencies, the investigator must discuss the event with the sponsor, sponsor's representative, and/or medical monitor prior to unblinding the subject's treatment assignment.

If the treatment assignment is unblinded for an individual subject, study personnel will be notified of that subject's treatment assignment without unblinding of the treatment assignments for the remaining subjects in the study. Thus, the overall study blind will not be compromised. If a subject's treatment assignment is unblinded, he or she may or may not be asked to withdraw from the study. The investigator will make this decision after consultation with the sponsor, sponsor's representative, or medical monitor.

4.6. Treatment Compliance

Investigational treatment will be administered at the site under the supervision of site staff. Study compliance with other procedures will be monitored for each subject based on attendance at scheduled visits.

4.7. Permitted and Prohibited Therapies

4.7.1. Permitted Therapies

Prescription medications that in the opinion of the investigator would not potentially interact with fentanyl or interfere with its respiratory effects were permitted during the course of this study.

4.7.2. Prohibited Therapies

The following medications are prohibited during this study:

- Any prescription medication that in the opinion of the investigator could potentially interact with fentanyl or interfere with its respiratory effects within 14 days prior to the first dose of study medication or during the course of this study.
- Enzyme altering drugs such as barbiturates, corticosteroids, phenothiazines, cimetidine, carbamazepine, etc., within 30 days prior to the first dose of study medication or during the course of this study.

Subjects are to abstain from consuming any of the following:

- Alcohol from 24 hours before surgery on Day 0 until 48 hours after treatment and inpatient assessments.
- Caffeine-containing foods and drinks (e.g. coffee, cola, Red Bull, chocolate, etc.) from 24 hours prior to surgery on Day 0 until 48 hours after treatment and inpatient assessments.
- Tobacco products or nicotine-containing products 24 hours before surgery on Day 0 until 48 hours after treatment and inpatient assessments.

4.8. Rescue Medication

Prior to the Treatment Period, ibuprofen 400 mg will be allowed orally every 4 to 6 hours as needed for pain before the regional anesthetic infusion (continuous popliteal sciatic block) is discontinued. If the subject is unable to tolerate 400 mg ibuprofen or if there is insufficient pain relief, then subject may receive supplemental analgesia with a hydrocodone/acetaminophen combination. One to two hydrocodone/acetaminophen 5/325-mg tablets may be administered every 4 to 6 hours as needed for moderate to severe pain, up to a daily limit of 8 to 10 tablets. If the subject cannot tolerate the hydrocodone/acetaminophen or if there is insufficient pain relief, then 30 mg ketorolac tromethamine (eg, Toradol®) may be administered intravenously or intramuscularly every 6 to 8 hours as needed for pain. The total daily (24-hour) dosage of ibuprofen medication should not exceed 2400 mg; the total daily dose of acetaminophen should not exceed 3250 mg; the total daily dose of ketorolac should not exceed 90 mg.

During the Treatment Period (after the regional anesthetic infusion is discontinued), ibuprofen 400 mg will be allowed orally every 4 to 6 hours as needed for rescue medication. If subjects are unable to tolerate 400 mg ibuprofen or if there is insufficient pain relief, 30 mg of ketorolac tromethamine (i.e., Toradol®) may be administered intravenously or intramuscularly every 6 to 8 hours as needed for pain. The total daily (24 hour) dosage of ibuprofen medication should not exceed 2400 mg and ketorolac should not exceed 90 mg.

Subjects will be allowed to use assigned study medication for primary rescue medication no more frequently than 4 hours from previous study medication dose and no more than 6 times in a 24-hour period. Subjects will be encouraged to wait for at least 1 hour after the first dose of study drug before receiving rescue medication to allow time for the study drug to exert its pharmacologic effect.

The rescue medication, specific reason for use, and the time since the last scheduled dose of IP will be captured on the appropriate CRF. Pain intensity assessments will be recorded immediately before each dose of rescue analgesia during the Treatment Period.

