An electrocardiogram (ECG) will be conducted after surgery but before the first dose of the study drug and serve as a baseline for comparison to subsequent tracings. The time of the NRS assessment before study drug administration is defined as Baseline; the time of administration of the first dose of study drug is defined as Time 0. Study drug will be provided by blinded study personnel in a predefined manner to ensure adequate blinding and appropriate dosing regimens for the active drug and placebo. Subjects should not have anything orally except room-temperature water within 15 minutes of each dose. The Treatment Period will continue through 48 hours after Time 0. Pulse oximetry will be continuously monitored and SpO₂ data will be recorded at select time points including baseline before first dose of study drug and 90 minutes and 12, 24, and 48 hours after Time 0. Additional ECGs will be performed at 90 minutes, 12 hours, 24 hours, and 48 hours after Time 0.

Ibuprofen 400 mg will be allowed orally every 4 to 6 hours as needed for rescue medication after study drug treatment has begun. If subjects are unable to tolerate 400 mg ibuprofen or if there is insufficient pain relief, 30 mg of ketorolac tromethamine (i.e., Toradol®) may be administered intravenously or intramuscularly every 6 to 8 hours as needed for pain. The total daily (24 hour)

dosage of ibuprofen medication should not exceed 2400 mg and ketorolac should not exceed 90 mg.

During the Treatment Period, subjects will be allowed to use assigned study medication for primary rescue medication no more frequently than 4 hours from previous study medication dose and no more than 6 times in a 24-hour period. Subjects will be encouraged to wait for at least 1 hour after the first dose of study drug before receiving rescue medication to allow time for the study drug to exert its pharmacologic effect.

During the Treatment Period, subjects whose pain cannot be adequately managed (in the investigator's opinion) by a combination of study drug and rescue medication, or who develop unacceptable side effects during the study, will be discontinued from further study participation. Their pain will be managed according to usual standard of care at the investigator's discretion.

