Pain will be assessed on an 11-point Numeric Rating Scale (NRS) at Baseline before Time 0. Thereafter, subjects will rate their pain intensity (NRS) and pain relief (on a 5-point categorical scale) and record their assessments in an inpatient subject diary at scheduled times during the 48-hour period after Time 0 (at 2.5, 5, 15, 30, and 45 minutes, and 1, 1.5, 2, 3, 4, 5, 6, 7, 8, 12, 16, 20, 24, 32, 40, and 48 hours) and immediately before each use of each rescue analgesia during the Treatment Period. Time to perceptible and meaningful pain relief will be evaluated using the 2 stopwatch method (after the first dose only). Subjects will complete a subject's global evaluation of the study drug at the end of the Treatment Period (Day 3) before discharge from the study site.

[figure not shown]
If a subject discontinues the study prematurely, pain intensity, pain relief, and the subject's global satisfaction with study treatment should be assessed and recorded immediately before discontinuation.

Before discharge from the study site on Day 3, study personnel will dispense a prescription for outpatient pain medication (if not already dispensed) and subjects will be given an outpatient subject diary in which they will be instructed to record concomitant medications taken and adverse events (AEs) experienced after discharge. Subjects will also be instructed to return the outpatient subject diary to study personnel at the Follow up Visit, 7 ± 2 days after surgery.

The planned sequence and maximum duration of the study periods will be as follows:

- Screening Period: up to 28 days
- Surgical Period: Day 0
- Treatment Period: Days 1-3 (up to 9 hours post-surgery plus 48 hours of treatment and inpatient assessments)
- Follow-up: Day 7 ± 2 days (5 to 9 days after surgery) or early withdrawal

Subjects will be confined for approximately 72 hours at the study site for the Surgical and Treatment Periods. The maximum study duration for each subject is approximately 6 weeks

Figure 1: Study Design Schematic

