7.3. Treatment Period (Days 1-3)

The treatment period comprises Day 1 (Baseline before dosing) and Day 2 and 3 (48 hours after the first dose of study medication).

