7.3.1. Pre-randomization

On Day 1, the regional anesthetic infusion will be discontinued at approximately 3:00 AM. Thereafter, when subjects request pain medication, they will be asked to rate their pain intensity using an 11-point (0-10) Numeric Rating Scale (NRS). During the 9-hour period after discontinuation of the anesthetic block, subjects who experience a pain intensity rating of ≥ 4 on the NRS are eligible to be enrolled in the study. Subjects whose pain intensity ratings do not meet the minimum entry criteria within 9 hours after discontinuation of the regional anesthesia will not be eligible for enrollment and will receive routine postoperative care at the investigator's discretion. Pulse oximetry will be monitored continuously after the procedure as a safety measure.

When a subject's pain meets the pain intensity entry criteria (≥ 4 on the NRS), he or she will be eligible to begin the Treatment Period and will be randomized.

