An electrocardiogram (ECG) will be conducted after surgery but before the first dose of the study drug and serve as a baseline for comparison to subsequent tracings. The time of the NRS assessment before study drug administration is defined as Baseline; the time of administration of the first dose of study drug is defined as Time 0. Study drug will be provided by blinded study personnel in a predefined manner to ensure adequate blinding and appropriate dosing regimens for the active drug and placebo. Study drug will be administered by study subjects according to the directions provided by study staff. Subjects should not have anything orally except room-temperature water within 15 minutes of each dose. The Treatment Period will continue through 48 hours after Time 0. Pulse oximetry will be continuously monitored and SpO₂ data will be recorded at select time points including baseline before first dose of study drug and 30, 60 and 90 minutes and 12, 24, and 48 hours after Time 0. Additional ECGs will be performed at 90 minutes, 12 hours, 24 hours, and 48 hours after Time 0.

Ibuprofen 400 mg will be allowed orally every 4 to 6 hours as needed for rescue medication after study drug treatment has begun. If subjects are unable to tolerate 400 mg ibuprofen or if there is insufficient pain relief, 30 mg of ketorolac tromethamine (i.e., Toradol®) may be administered intravenously or intramuscularly every 6 to 8 hours as needed for pain. The total daily (24 hour) dosage of ibuprofen medication should not exceed 2400 mg and ketorolac should not exceed 90 mg.

During the Treatment Period subjects will be allowed to use assigned study medication for primary rescue medication no more frequently than 4 hours from previous study medication dose and no more than 6 times in a 24-hour period. Subjects will be encouraged to wait for at least 1 hour after the first dose of study drug before receiving rescue medication to allow time for the study drug to exert its pharmacologic effect.

During the Treatment Period, subjects whose pain cannot be adequately managed (in the investigator's opinion) by a combination of study drug and rescue medication, or who develop unacceptable side effects during the study, will be discontinued from further study participation. Their pain will be managed according to usual standard of care at the investigator's discretion.

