7.3 Handling of Missing Data

7.3.1 Handling of Missing Data for Efficacy Assessments

Use of Rescue Medication: Any pain intensity or pain relief score occurring within 4 hours after a subject has taken rescue medication for pain will be replaced by the last pain intensity or pain relief score prior to that use of rescue medication. If a second rescue medication for pain is used within that 4 hour duration, the pain intensity or pain relief scores from the time of the first rescue medication will be replaced by the assessment prior to the second rescue medication for the next 4

hours. The same method will be employed for a third and subsequent rescue medication.

Missing due to Dropouts: Missing values for pain intensity after a subject drops out of the study will be imputed as follows in the primary analysis:

- For SPID endpoints, the last available SPID (truncated SPID) will be used for analysis (e.g., if a subject dropped out after 32 hours of initiation of treatment, the truncated SPID calculated using timepoints up to 32 hours will be used as the post 32 hour timepoints like 40 hours and 48 hours).
- For TOTPAR endpoints, the last available TOTPAR (truncated TOTPAR) will be used for analysis
- For PID endpoints, the last available pain intensity will be used to impute the missing pain intensity and to calculate the PID

In addition, a sensitivity analysis using 1) missing as missing (i.e., no imputation) for dropouts and 2) multiple imputation will be performed for the primary endpoint to explore the impact of missing data after a subject drops out. The details of the sensitivity analysis are described in [Section 7.4](#).

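### Protocol 4.8 opens NSAID rescue at block stop, but Protocol 3.1 and SAP 2.2 open it only after study drug starts; SAP 7.3.1 lacks a Time 0 condition, so pre-dose rescue could overwrite early pain scores

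*Protocol*

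**What the plan says.** Protocol 4.8 has two rescue paragraphs. The first covers the time while the block infusion is running. The second begins: "During the Treatment Period (after the regional anesthetic infusion is discontinued), ibuprofen 400 mg will be allowed orally every 4 to 6 hours". It then allows ketorolac if ibuprofen is not tolerated or not sufficient. Both paragraphs put the boundary at block stop.

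Protocol 3.1 puts it later: "Ibuprofen 400 mg will be allowed orally every 4 to 6 hours as needed for rescue medication after study drug treatment has begun". The synopsis has the same sentence, and SAP 2.2 allows ibuprofen "as needed for rescue medication after study drug treatment has begun".

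The block is stopped at about 3:00 AM on Day 1 (Protocol 7.3.1), and the first dose may follow within 9 hours, ± 10 minutes (Protocol 7.3.2). Table 2, note j, tells subjects to ask for medication as soon as they feel pain after block stop. Protocol 7.3.1 says what happens then: "Thereafter, when subjects request pain medication, they will be asked to rate their pain intensity". A subject who rates 4 or more is randomized.

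SAP 7.3.1 handles rescue as follows: "Any pain intensity or pain relief score occurring within 4 hours after a subject has taken rescue medication for pain will be replaced". The replacement is the last score before that rescue dose. The rule does not mention Time 0.

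**The concern.** Consider a subject who asks for medication after block stop and rates pain at 3. Protocol 4.8 allows ibuprofen; Protocol 3.1 does not. Two sites, or two nurses at one site, could act differently and both point to the protocol.

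The analysis rule has a matching gap. If that subject reaches NRS 4 and is dosed within 4 hours of the ibuprofen, the first post-dose scores fall inside the replacement window. A programmer who applies SAP 7.3.1 as written replaces them with a rating made before study drug, and those scores then carry no treatment effect. The carried rating is 3 or less and the baseline is 4 or more, so each replaced time point shows a fixed improvement of at least 1 point, on placebo as well as on fentanyl. Another programmer, reading SAP 2.2, would replace nothing. The endpoints exposed are SPID-4, SPID-8 and the early PID and pain intensity time points.

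**Working it through.** The plan gives no figure to reproduce here. The check compares the texts and then applies the SAP rule to the SAP grid.

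**Does the term Treatment Period reconcile the sections?** Protocol 7.3 counts the pre-dose baseline in it: "The treatment period comprises Day 1 (Baseline before dosing) and Day 2 and 3 (48 hours after the first dose of study medication". The sequence of periods in Protocol 3.1 also includes a pre-dose stretch: "up to 9 hours post-surgery plus 48 hours of treatment and inpatient assessments". Protocol 7.3.1 starts the period at qualification: "he or she will be eligible to begin the Treatment Period and will be randomized". The design paragraph in 3.1 labels it as 48 hours. The last two readings would bring 4.8 into line with 3.1; the first two would not. The parenthesis in 4.8 itself names block stop.

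**How much would be replaced?**

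Inputs:
- 21 nominal post-dose times in SAP 7.9.5: 0.0417, 0.0833, 0.25, 0.5, 0.75, 1, 1.5, 2, 3, 4 hours, and so on to 48.
- SPID weights in SAP 7.9.7: the hours since the preceding time point.
- The 4-hour window in SAP 7.3.1.
- Baseline as defined in SAP 7.1 (last value before randomized treatment), left unchanged.
- Assumption: no second rescue dose inside the window.

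Let *g* be the hours from the rescue dose to Time 0. The score at time *t* is replaced if *t* ≤ 4 − *g*. The weights telescope from zero, so the replaced weight equals the last replaced time.

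| Dose before Time 0 | Scores replaced | Weight | SPID-4 | SPID-8 | SPID-48 |
|---|---|---|---|---|---|
| 1 h | 9 | 3 h | 3/4 = 75% | 3/8 = 37.5% | 3/48 = 6.3% |
| 2 h | 8 | 2 h | 2/4 = 50% | 2/8 = 25% | 2/48 = 4.2% |
| 3 h | 6 | 1 h | 1/4 = 25% | 1/8 = 12.5% | 1/48 = 2.1% |
| 3.5 h | 4 | 0.5 h | 0.5/4 = 12.5% | 0.5/8 = 6.3% | 0.5/48 = 1.0% |
| 4 h or more | 0 | 0 h | 0% | 0% | 0% |

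The 1 h row is the maximum on the nominal grid: any dose strictly before Time 0 leaves the 4 h score outside the window, and the next score back is at 3 h.

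**Scale on SPID-48.** With 3 hours replaced, each NRS point of difference between the carried and the observed score moves that subject's SPID-48 by 3 units. That is 3/100 = 0.03 of the SD of 100 assumed in the synopsis.

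**Dilution of the arm difference.** The documents do not say how many subjects would be affected. Assume 10% are, by a dose 1 to 3 hours before Time 0, with an arm difference that is constant over time. The difference then shrinks by 0.10 × weight share:
- SPID-4: 0.10 × 25% = 2.5% to 0.10 × 75% = 7.5%
- SPID-8: 0.10 × 12.5% = 1.3% to 0.10 × 37.5% = 3.8%
- SPID-48: 0.10 × 2.1% = 0.2% to 0.10 × 6.3% = 0.6%

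**With a Time 0 condition**, a pre-dose rescue replaces 0 of 21 scores.

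**The case against.** The best defence is that rescue was always meant to follow Time 0, and much of the text supports it. SAP 2.2 says so. SAP 7.9.16 counts rescue over 0 to 24 and 0 to 48 hours, and SAP 7.9.17 measures time to rescue from Time 0. Protocol 7.3.1 gives no NSAID step between block stop and dosing. The rest of 4.8 presupposes dosing: it asks the site to record the time since the last scheduled study drug dose, which does not exist before Time 0. The replacement rule also covers pain relief, which is first scored after Time 0, so for a pre-dose rescue that half of the rule has nothing to carry. All of this stands as evidence of intent.

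The effect also needs several steps in a row: a request at NRS below 4, an NSAID given, NRS reaching 4 and dosing within 4 hours, the dose flagged as rescue, and the rule programmed literally. That stands too, as does the point that Protocol 8.5.3.2 plans no formal inference on secondary endpoints.

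What the defence does not remove is the wording of 4.8. It names block stop explicitly, and its preceding paragraph uses the same boundary. Nor does SAP 7.3.1 state the condition that SAP 7.9.17 states.

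**Conclusion.** The conflict over when rescue opens is real and lies in text that sites act on. The missing Time 0 condition in SAP 7.3.1 is a gap on a literal reading, not a declared intention. Severity is minor. In an affected subject at most 75% of SPID-4, 37.5% of SPID-8 and 6.3% of SPID-48 weight is replaced. These figures assume the nominal grid and a single rescue dose; frequency is unknown.

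A reader might infer more than the documents support:
- **That the primary endpoint is compromised.** The SPID-48 share is small, and the dilution is 0.2 to 0.6% per 10% of subjects affected.
- **That one arm is favoured.** The dose precedes randomization, so its effect is balanced in expectation. Randomization is stratified by center (SAP 2.4.2) and site is in the model (SAP 8.2.1), so differing site practice does not confound treatment.
- **That the baseline score is overwritten too.** SAP 7.1 fixes baseline as the last value before treatment.
- **That other SAP rules need repair.** The stopwatch censoring in SAP 7.9.11, 7.9.14 and 7.9.15 and the time to rescue in 7.9.17 already run from the first dose.
- **That study drug would trigger replacement, because 4.8 also lets it serve as rescue.** SAP 7.9.17 identifies rescue from the Concomitant Medications eCRF, which keeps study drug apart.

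**What to change.** 1. Protocol 4.8, second paragraph: replace the parenthesis about the infusion with *after the first dose of study drug*, to match 3.1 and the synopsis. If the sponsor does want an NSAID available between block stop and Time 0, it should say so consistently in the synopsis, 3.1, 4.8 and 7.3.1 instead.
2. SAP 7.3.1: add *Only rescue medication taken after Time 0 triggers replacement.* This is worth having even if 4.8 stays as it is, because analgesics allowed during the infusion also appear under the rescue heading and could fall within 4 hours of Time 0.
3. Optional: state in SAP 7.3.1 that study drug is not rescue medication for this rule.

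Cost: the SAP change is one sentence before database lock. It needs no new data, since SAP 7.9.17 already requires the time of rescue relative to Time 0. The protocol change needs a formal amendment with sponsor approval, investigator signature and IRB approval (Protocol 10.1), so it is best bundled with another amendment. Once dosing is complete, only the SAP sentence can still have an effect.
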